5.0 EXPERIMENTAL PROTOCOL

Protocol Design:

This is a single institution, randomized, placebo-controlled clinical study. There will be 3 cohorts: control group, pre-isolation nitrite infusion, and a post-isolation (reinfusion) cohort.

After induction of general anesthesia with propofol (1-1.5 mg/Kg), tracheal intubation, the establishment of central venous access, invasive monitors and maintenance anesthesia with sevoflurane (1-1.5 minimum alveolar concentration) in 50:50 oxygen: air, infusions will be administered based on the randomization assignment.

I. Control Group A placebo (saline infusion) will be administered during the pre-isolation phase and during the reinfusion phase.

II. Pre-Isolation Infusion Group

[figure not shown]

Figure 1: Pre-isolation group schematic: Sodium nitrite will be initiated (pre-isolation infusion group) during the pre-isolation phase. Saline will be administered during the reperfusion period.

III. Post-Isolation (Reinfusion) Group

[figure not shown]

Figure 2: Reinfusion group schematic: Saline will be administered during the pre-isolation period. Sodium nitrite infusion will be initiated just prior to the reinfusion.

For all 3 groups:

Intraoperative arterial and venous blood samples (BS) will be drawn immediately prior to initiation of the infusion (BS1), 5 min prior to infusion of Islet Cells (BS2), 20 min after infusion of Islet Cells (BS3), and 40 min after infusion of Islet Cells (BS4).

Postoperative blood samples will be obtained 24, 48, 72 and 96 hours after the completion of surgery.

Results of routine lab work performed at the routine 3 month follow-up visit will be collected.

Procedure for Sample collection (email from [name] 6/28/16) – to be performed by lab tech in BMR

- 1) *Transferring blood to Eppendorf tubes,*
- 2) *Centrifuging (using a table top min-fuge which we can provide),*
- 3) *Transferring plasma to 4 other vials (1 containing a pre-made solution, which we can provide) and flash freezing all vials in liquid N₂*
- 4) *Taking some of the red cell pellet and adding to vials (containing pre-made solution that we can provide) and flash freezing all vials in liquid N₂*
- 5) *All samples need to be stored at -80C.*

Primary Endpoints:

- Markers of pancreatic function:
 - Blood glucose levels
 - HbA1c levels pre-operatively and at the 3 month post-operative visit
 - Exogenous insulin use
 - Measured from blood samples 24, 48, 72, 96 hours post op & at 3 months post op

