7.0 STATISTICAL CONSIDERATIONS

Primary Study Variables include: Demographics (age, gender, pre-operative weight, pre-operative BMI,

General Data Analysis: All anthropometric data will be compared using unpaired Student's t-test. Length of stay data will be compared using Cox proportional hazard

analysis. All other data will be compared using one-way repeated measures ANOVA with post-hoc analysis by unpaired Student's t-test or Chi Square analysis as appropriated. For all comparisons, a value of $p < 0.05$ will be considered significant.

This is a pilot study. We plan to enroll 10 patients in each of the 3 arms of this study (total N=30).

Study Population Availability: Approximately 8-10 patients present to UAB for this procedure annually. Potential study subjects will be identified by [name] and his clinic team.

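### Section 7.0 gives its repeated measures ANOVA no missing-data rule and no sphericity correction, so incomplete patients drop out of it and its time and arm-by-time tests can exceed 5%

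*Combined protocol and SAP*

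**What the plan says.** Section 7.0 (Statistical Considerations, General Data Analysis) sets aside anthropometric data and length of stay, then states: "All other data will be compared using one-way repeated measures ANOVA", "with post-hoc analysis by unpaired Student's t-test or Chi Square analysis as appropriated". On the error level: "For all comparisons, a value of $p < 0.05$ will be considered significant". On size: "We plan to enroll 10 patients in each of the 3 arms of this study (total N=30").

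Section 5.0 (Experimental Protocol) gives the time grid. "Postoperative blood samples will be obtained 24, 48, 72 and 96 hours after the completion of surgery". The primary endpoint list says: "Measured from blood samples 24, 48, 72, 96 hours post op & at 3 months post op". The last value has a different source: "Results of routine lab work performed at the routine 3 month follow-up visit will be collected". HbA1c is on a shorter grid: "HbA1c levels pre-operatively and at the 3 month post-operative visit".

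The sampling table at the end of section 5.0 marks blood glucose at nine times (BS1 to BS9), exogenous insulin at the five postoperative times and HbA1c at two.

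No section gives a sphericity test or correction, a covariance structure, a mixed model, an imputation method or any other missing-data rule. The plan also does not say which times enter one ANOVA, or whether arm is a factor in it.

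**The concern.** Two properties of classical repeated measures ANOVA matter here, and the plan deals with neither.

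First, it uses only patients with a value at every time in the analysis. If the five primary times are analysed together, a patient without the routine 3-month result also leaves the 24 to 96 hour part of that ANOVA, although those samples were taken. With 10 patients per arm, each such loss is a tenth of an arm. If the patients lost differ in outcome, the result is biased as well as less precise.

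Second, its within-patient F tests assume sphericity: the difference between any two times has the same variance. Four samples one day apart, then one about three months later, make that hard to believe. When it fails, the uncorrected time and arm-by-time tests reject too often. Arm-by-time is the natural test of whether glucose or insulin use runs a different course under nitrite, and section 1.0 says that further studies will follow if the data support the hypotheses.

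**Working it through.** **Inputs from the documents.** Three arms of 10; five primary times; nine glucose times; two HbA1c times; 5% level. **Not in the documents, so assumed:** within-patient correlations, SDs and missing rates.

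**1. The plan's own figure.** The method was run on 20,000 simulated null trials (3 × 10 patients, five times, complete data, sphericity true). Rejection rates were 5.1% for time, 5.2% for arm-by-time and 4.9% for arm. The simulation standard error is √(0.05 × 0.95 / 20,000) = 0.15 percentage points. The stated 5% is reproduced when the assumption holds.

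**2. Patients left in the ANOVA.** With missing rate m per sample, independent over k samples, expected complete cases = 30 × (1 − m)^k.

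| m | k = 5 | k = 9 (glucose) |
|---|---|---|
| 2% | 30 × 0.98^5 = 27.1 | 25.0 |
| 5% | 30 × 0.95^5 = 23.2 | 18.9 |
| 10% | 30 × 0.90^5 = 17.7 | 11.6 |

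If only the 3-month value is missing, in 10% or 20% of patients, 27 or 24 remain. In the second case 6 patients × 4 early samples = 24 of the 120 early values are collected but not used by the ANOVA.

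**3. Why sphericity is doubtful.** With equal SD σ, the variance of a difference between two times is 2σ²(1 − ρ). Take a one-day correlation of 0.6, decaying as 0.6^days over the first four samples, and 0.1 with month 3:
- 24 v 48 h: 2σ²(1 − 0.6) = 0.8σ²
- 24 v 96 h: 2σ²(1 − 0.6³) = 1.57σ²
- 24 h v 3 months: 2σ²(1 − 0.1) = 1.8σ²

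Sphericity needs these to be equal.

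**4. Error rate of the uncorrected tests, five times, nominal 5%.** Correlation is ρ^(days apart), with 3 months taken as day 90. Equal-SD ranges are with and without a constant patient component of 0.3. Epsilon is 1 under sphericity.

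| Assumed setting | Epsilon | Time | Arm-by-time |
|---|---|---|---|
| Equal SDs, ρ = 0.3 | 0.94 | 5.0–5.4% | 5.4–5.5% |
| Equal SDs, ρ = 0.5 | 0.84 | 5.8–6.3% | 6.2% |
| Equal SDs, ρ = 0.7 | 0.68 | 7.3–7.4% | 7.8–7.9% |
| Equal SDs, ρ = 0.9 | 0.41 | 9.7–9.9% | 10.9–11.4% |
| 3-month SD × 1.5, ρ = 0.5 to 0.9 | 0.68–0.35 | 7.1–10.6% | 7.8–12.9% |
| 3-month SD × 2, ρ = 0.5 to 0.9 | 0.53–0.31 | 8.8–11.5% | 9.2–13.3% |

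A separate run used the step 3 correlations, with the 3-month SD at 1, 1.5 and 2 times the early SD. It gave 6.2%, 7.4% and 8.7% for time, and 6.7%, 8.0% and 9.8% for arm-by-time.

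On the nine-time glucose grid (intraoperative clock times assumed, ρ = 0.3 to 0.9, equal SDs) the rates were 9.0–13.0% and 9.6–15.2%.

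Read literally, a one-way model has time as its only factor. With 30 patients in one group and equal SDs, its time test ran at 6.0%, 7.5% and 10.0% for ρ = 0.5, 0.7 and 0.9.

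**5. Tests that are not inflated.** Arm main effect: 4.6–5.3% throughout. Unpaired t-test at a single time, under the step 3 correlations: 4.8–5.2%. HbA1c: about 5%, because two times give one difference and sphericity holds automatically.

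**6. With a Greenhouse-Geisser correction, five times.** Equal SDs: 3.9–4.9% for time and 4.1–5.1% for arm-by-time. Unequal SDs: at most 5.6%.

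**The case against.** The strongest reply is that the tests which compare arms are mostly sound. A literal one-way model contains no arm-by-time term, and its time test is not a treatment comparison. The arm comparisons that section 7.0 does name, the post-hoc unpaired t-tests, hold their level at each time. They use every patient with a value at that time, so a missed 3-month visit does not remove anyone from a 24-hour t-test. This stands, and it limits the point to the ANOVA itself.

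Several stronger readings are tempting, and the documents do not support them:

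- **That the trial will lose patients and will exceed 5%.** No missing rate or correlation is given. With complete data nobody is dropped, and at a correlation of 0.3 with equal SDs the five-time excess is close to nil.
- **That the 3-month gap is the cause.** Under the step 3 correlations, dropping the 3-month value still gives about 6.2% to 6.5%, because correlation that decays over 24 to 96 hours already breaks sphericity. The larger figures need higher correlation or an assumed larger 3-month SD.
- **That patients whose islets are never infused are excluded according to outcome.** No section describes such a patient. Samples timed from infusion would be undefined for that patient, and a mixed model would not supply them.

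It can also be said that this is a pilot with many endpoints, so no covariance model will deliver an overall 5%. That is true, but the plan still calls p < 0.05 significant for every comparison, and this gap can be closed in the wording alone.

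**Conclusion.** The point holds as a gap in specification with a conditional cost. Section 7.0 names a method that discards incomplete patients and relies on sphericity, and provides for neither.

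The loss is about 3, 7 or 12 of 30 patients from a five-time ANOVA at 2%, 5% or 10% missing per sample, and none if no values are missing.

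On the five primary times, the time test, and the arm-by-time test if arm is included, range from about 5% (correlation 0.3, equal SDs) through 6% to 7% (0.6). With higher correlation or a larger 3-month SD they are mostly 8% to 12%, with extremes of 7.1% and 13.3%. These figures rest on assumed correlations, SDs and missing rates, so they show what can happen, not what will. They do not extend to the arm main effect, HbA1c or the single-time t-tests.

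**What to change.** In section 7.0, replace the repeated measures ANOVA for continuous serial outcomes with a linear mixed model fitted to all available values of all randomised patients. Include arm, time and arm-by-time, use Kenward-Roger degrees of freedom, and take the arm contrasts at each time, with 95% confidence intervals, from that model.

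For the five postoperative times use an unstructured covariance (5 × 6 / 2 = 15 parameters), and state in advance a simpler heterogeneous structure to use if it does not converge. For the nine-time glucose series use the simpler structure from the start: an unstructured one needs 9 × 10 / 2 = 45 parameters from 30 patients.

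If the ANOVA is kept, the minimum is to apply a Greenhouse-Geisser correction. That brings the within-patient tests back to about 4% to 5%, but does not recover dropped patients.

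The cost is SAP wording and modest programming, with no added patients, samples or visits. The downsides are more covariance parameters, fewer denominator degrees of freedom, and reliance on values being missing at random, so bias can remain if missingness depends on unobserved outcome.

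### The unpaired post-hoc t-test in section 7.0 does not match the one-way repeated measures ANOVA it follows, and would be mis-sized and, with positive correlation, weak if used between times in the same patients

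*Combined protocol and SAP*

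**What the plan says.** Under General Data Analysis, section 7.0 assigns unpaired t-tests to anthropometric data and Cox analysis to length of stay. Everything else falls under one sentence: "All other data will be compared using one-way repeated measures ANOVA with post-hoc analysis by unpaired Student's t-test or Chi Square analysis as appropriated". The threshold is that "a value of $p < 0.05$ will be considered significant"; sidedness is not stated. Section 7.0 names no paired test, no arm factor and no arm-by-time term, and does not say which levels the post-hoc tests compare.

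The design has three parallel groups: "There will be 3 cohorts: control group, pre-isolation nitrite infusion, and a post-isolation (reinfusion) cohort". On size, section 7.0 says "We plan to enroll 10 patients in each of the 3 arms of this study (total N=30", and the only justification given is "This is a pilot study".

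The data are repeated within patient. Section 5.0 has intraoperative draws and then "Postoperative blood samples will be obtained 24, 48, 72 and 96 hours after the completion of surgery", plus a 3-month visit. The primary endpoints include "HbA1c levels pre-operatively and at the 3 month post-operative visit", and the list of pancreatic function markers ends with "Measured from blood samples 24, 48, 72, 96 hours post op & at 3 months post op". By the sampling table in section 5.0:

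- glucose is taken at nine times (BS1 to BS9);
- C-peptide at six (BS1, BS5 to BS9);
- exogenous insulin at five (BS5 to BS9);
- HbA1c at two (BS1, BS9).

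**The concern.** A post-hoc test locates differences among the levels of the factor just tested. In a one-way repeated measures ANOVA those levels are occasions in the same patients. An unpaired t-test assumes that the two sets of values come from different patients. Read literally, the plan uses the pairing in the first step and discards it in the second.

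For glucose, C-peptide and exogenous insulin, each with five or more times, a significant ANOVA could then be followed by no significant pair, and a real change over time could be missed in arms of 10. On the other reading, where the post-hoc test compares arms, the t-test is sound but the ANOVA in front of it says nothing about arms. Two analysts following this sentence could run different analyses.

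**Working it through.** **Inputs.** From section 7.0: 10 patients per arm, three arms, 0.05 threshold. From the sampling table in section 5.0: five to nine times for the repeated markers. Assumed, because the plan gives no figure: two-sided tests, equal SD at each time, normal values, within-patient correlation ρ of 0.3, 0.5 and 0.7 (with 0 and −0.2 as checks), and a true change of 0.8 SD.

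**The plan's own figure.** 3 × 10 = 30, as stated. There is no power calculation to reproduce.

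**Reading A: time against time in the same n patients.**

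- SE used by the unpaired test: SD × √(2/n).
- True SE of the mean change: SD × √(2(1 − ρ)/n).
- Ratio of the two: 1/√(1 − ρ).

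For n = 10 and SD = 1 the unpaired SE is √0.2 = 0.447. The true SE is √0.14 = 0.374 at ρ = 0.3, √0.10 = 0.316 at ρ = 0.5 and √0.06 = 0.245 at ρ = 0.7. The ratios are 1.20, 1.41 and 1.83.

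Simulated rejection rates (200,000 runs per setting, n = 10, two times):

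| ρ | No change: unpaired | No change: paired | 0.8 SD change: unpaired | 0.8 SD change: paired |
|---|---|---|---|---|
| −0.2 | 7.1% | 4.9% | 0.40 | 0.31 |
| 0 | 5.0% | 5.0% | 0.40 | 0.36 |
| 0.3 | 2.3% | 5.0% | 0.38 | 0.48 |
| 0.5 | 1.0% | 5.0% | 0.37 | 0.62 |
| 0.7 | 0.2% | 5.1% | 0.35 | 0.83 |

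With all 30 patients pooled and a 0.5 SD change, power is 0.48 unpaired against 0.61 paired (ρ = 0.3), 0.47 against 0.76 (ρ = 0.5) and 0.47 against 0.93 (ρ = 0.7).

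The two-step sequence was also simulated: five times, one arm of 10, means rising linearly by 0.8 SD in total. Among runs with a significant ANOVA, no unpaired pair was significant in about 5%, 21% and 45% at ρ = 0.3, 0.5 and 0.7.

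**Reading B: arm against arm at one time.** The samples are independent patients. With 10 per arm the unpaired t-test rejects 4.9% of the time under no effect, so it holds its level. The ANOVA is now the part that does not fit. A time-only ANOVA was run on 30 patients at five times with ρ = 0.5, with one arm shifted by 1 or 2 SD at every time. It rejected in 4.9% and 4.8% of runs, so it did not detect the arm difference. A two-arm t-test on patient means had power 0.78 and above 0.99 for the same shifts.

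**The case against.** The strongest reply is that the plan never says the post-hoc tests compare times. The preceding sentences on anthropometrics and length of stay can sensibly mean only comparisons between groups, the hypotheses concern nitrite, and the arms are independent. On that view the word unpaired was chosen for arm comparisons, where it is right. This stands to the extent that the documents do not establish that any patient's samples will be treated as if they came from different patients. It does not rescue the sentence, because the named ANOVA has no arm factor for such tests to follow.

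Several stronger readings are tempting, and the documents do not support them.

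- *That the HbA1c pair is mis-tested.* With two values, the repeated measures ANOVA is already the paired t-test (F = t²), and a two-level factor needs no post-hoc test.
- *That chi-square is wrong.* Its natural use is postoperative incidence of diabetes, one result per patient, compared between arms. A problem arises only if a repeated yes/no outcome is compared over time.
- *That 95% intervals are affected.* Section 7.0 specifies only a p-value threshold.
- *That wrong variability estimates would pass to a later trial.* An unpaired test leaves the SD at each time unchanged, and the plan does not say its standard error will be carried forward.

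Two limits also stand. The power loss needs positive correlation: at zero the unpaired test loses nothing (0.40 against 0.36), and at −0.2 it rejects too often. And a change over time within one arm, or in all patients pooled, is not the nitrite-against-saline question. With positive correlation the error is conservative and does not create false positives.

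**Conclusion.** The point holds in conditional form. The ANOVA and its post-hoc test address different factors under either reading, and that follows from the sentence itself. The figures for reading A (standard error inflated 1.2 to 1.8 times, type I error of about 2% to 0.2%, and the power loss in the table) rest on an assumed correlation of 0.3 to 0.7. That is plausible for repeated laboratory values, but the plan does not document it. They apply to markers with three or more times (glucose, C-peptide, exogenous insulin), not to HbA1c. Under reading B the unpaired test needs no change, but the model in front of it does. The sentence should be corrected before analysis; nothing in the trial's conduct is affected.

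**What to change.** Replace the post-hoc wording in section 7.0 with text such as: *Comparisons between times in the same patients use paired or model-based contrasts from the repeated-measures model, or McNemar's test if a repeated yes/no outcome is compared over time. Unpaired t-tests and chi-square tests are used only between randomised arms, at one time or on within-patient change (for HbA1c, 3-month minus pre-operative). Arm comparisons of repeated measures come from a model that includes arm.* An arm-by-time repeated measures ANOVA or a mixed model would serve.

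The cost is one or two sentences, with no new data, patients or procedures. The downside is small: a paired t-test on 10 patients has 9 degrees of freedom instead of 18, and only patients with both values contribute to it. In the simulations with correlation of 0.3 to 0.7, pairing more than made up for the lost degrees of freedom; at zero correlation it cost a little power.

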- Decrease in reperfusion injury
- Incidence of diabetes post-operatively

Intraoperative blood samples will be analyzed for serum and methemoglobin levels and biochemical markers of oxidative and nitrosative stress, including plasma and hepatic 3-nitrotyrosine, oxidized lipids (isoprostanes, 8-epi-PGF₂α), protein carbonyls and the NO-metabolites, nitrite, nitrate, S-nitrosothiols, C-N-nitroso compounds and heme nitrosyls. If the above processing is not part of the costs, and assuming 30 patients, each with 6 blood draws then running assays for plasma and red cell NOx, C-peptide levels, circulating pro-inflammatory chemokines/cytokines and perform immunophenotyping of monocytes and neutrophils by flow cytometry and mRNA accumulation.

	Sample Name	Blood Glucose	HbA1c	Insulin level exogenous	RF	C-peptide	Circ pro-inflammatory chemokine / cytokines	Immunophenotyping monocytes and neutrophils	mRNA				
Intraoperative													
Prior to infusion	BS1	X	X			X	X	X	X				
5 min prior to Islet cell infusion	BS2	X											
20 mins after infusion of Islet cells	BS3	X											
40 mins after infusion of Islet cells	BS4	X											
Post-op													
24 hours	BS5	X		X		X	X	X	X				
48 hours	BS6	X		X		X	X	X	X				
72 hours	BS7	X		X		X	X	X	X				
96 hours	BS8	X		X		X	X	X	X				
Follow up													
Clinic visit 3 months post-op	BS9	X	X	X		X	X	X	X				

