8.0 SAFETY MONITORING

The intraoperative anesthetic and postoperative intensive care management of these patients will be the responsibility of the anesthesiologist or critical care physician, respectively.

Possible Adverse Events: Primary clinical concerns include the formation of methemoglobin and inhibition of platelet function. Phase I studies of sodium nitrite infusion have been completed in more than 80 normal human volunteers at the doses planned for this trial with no observed toxicity (e.g., no clinically significant increases in methemoglobin or hypotension). Nevertheless, plasma methemoglobin will be measured throughout the intraoperative and immediate postoperative periods. The study drug will be discontinued should methemoglobin levels increase to 5% or greater. Parameters related to coagulation and bleeding will be monitored per standard of care. Adverse coagulation or excessive bleeding will lead to immediate cessation of study drug. Based on our prior experience with inhaled NO (**Lang REF**), we do not anticipate increased bleeding relative to placebo and anticipate that metHb levels will remain $< 5\%$ for the duration of nitrite administration

Assessment of Level of Risk: Very low (numerous studies have established safety of nitrite infusion).

Oversight of this investigation will be provided by the PI, surgeon, and co-investigators. They will be responsible for all aspects of the conduct of the trial.

Safety oversight will be provided by the Data and Safety Monitoring Board (DSMB).

9.0 Adverse Events Reporting: This study poses minimal risk.

10.0 References:

4. XIAP overexpression in islet beta-cells enhances engraftment and minimizes hypoxia-reperfusion injury. Emamaullee J, Liston P, Korneluk RG, Shapiro AM, ...

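### Methemoglobin, a named safety concern with a 5% patient-level limit, has no analysis of its own; the default p<0.05 tests cannot support a safety conclusion with 10 patients per arm

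*Combined protocol and SAP*

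**What the plan says.** Section 8.0 (Safety Monitoring) states: "Primary clinical concerns include the formation of methemoglobin and inhibition of platelet function". It adds that "plasma methemoglobin will be measured throughout the intraoperative and immediate postoperative periods" and sets a patient-level rule: "The study drug will be discontinued should methemoglobin levels increase to 5% or greater". The investigators "anticipate that metHb levels will remain" below 5% while nitrite is given, and a DSMB has safety oversight.

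Section 5.0 (Experimental Protocol) also lists methemoglobin among the laboratory variables: "Intraoperative blood samples will be analyzed for serum and methemoglobin levels and biochemical markers of oxidative and nitrosative stress". The sampling table in that section has no methemoglobin column.

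Section 7.0 (Statistical Considerations) gives separate methods for anthropometric data and for length of stay. Everything else goes to one rule: "All other data will be compared using one-way repeated measures ANOVA with post-hoc analysis by unpaired Student's t-test or Chi Square analysis as appropriated", with p<0.05 as the criterion for every comparison. Each of the three arms has 10 patients, so 20 are assigned to nitrite. Section 9.0, on adverse event reporting, says only that risk is minimal. No section says how patients at or above 5%, or stopped for methemoglobin, will be counted or reported.

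**The concern.** The safety question is about individuals: how many patients reach 5%, and how high do levels go? The planned output is a significance test between arms, which answers another question. A few high values raise an arm's mean but raise its SD more, so the t-test can miss them. A small rise that leaves every patient well under 5% can be significant. The proportion test allowed by the same sentence has little power with 10 per arm.

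Section 1.0 calls this a pilot whose results decide whether further studies follow, so its safety statement will carry forward. The risk is that a p-value above 0.05 is taken as evidence of no methemoglobin problem.

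**Working it through.** **Inputs from the documents.** 10 patients per arm, three arms (3 × 10 = 30, which agrees with the stated total); significance at p<0.05, taken as two-sided; a patient-level limit of 5%. The plan gives no power, event rate, mean or SD for methemoglobin, so it has no figure of its own to reproduce.

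**Assumptions.** Control mean 1.0%; between-patient SD 0.3 and within-patient SD 0.2 points, so total SD = √(0.3² + 0.2²) = √0.13 = 0.36; crossers at 6%. SDs of 0.5 and 0.8 are also shown. As written, the one-way repeated measures ANOVA has no arm factor, so the comparison between arms rests on the post-hoc tests. Those are what is checked here.

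**1. t-test with isolated crossers.** Compare one nitrite arm with control at one sample time. Put k patients at 6% and the rest at their expected value. Then t = difference / √((s² + 0.13)/10), where s² is the nitrite-arm variance. Scatter among the other nitrite patients is left out; it would lower t slightly. The critical value on 18 df is 2.10.

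- One crosser, the other nine at 1.0%: difference 0.5; s² = (4.5² + 9 × 0.5²)/9 = 2.50; t = 0.5/0.513 = 0.97.
- Two crossers, the other eight at 1.0%: difference 1.0; s² = (2 × 4² + 8 × 1²)/9 = 4.44; t = 1.0/0.676 = 1.48. With SD 0.8 (0.64 in place of 0.13), t = 1.0/0.713 = 1.40.

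In simulation these two cases are significant in about 0.04% and 0.7% of trials. With SD 0.3 to 0.5 and peaks of 5.5% to 7%, the ranges are under 1% for one crosser and 0.03% to 4% for two. With three crossers the range is 17% to 26%.

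**2. t-test when the other patients also rise.** Two crossers at 6%:

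- Other eight at 1.3%: difference 1.24; s² = (2 × 3.76² + 8 × 0.94²)/9 = 3.93; t = 1.24/0.637 = 1.95; significant in about 25% of trials.
- Other eight at 1.5%: difference 1.40; s² = (2 × 3.6² + 8 × 0.9²)/9 = 3.60; t = 1.40/0.611 = 2.29; significant in about 71%.

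**3. Rise of 0.5 points with nobody near 5%.** Noncentrality is (0.5/SD) × √5, and power comes from the noncentral t on 18 df.

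| SD | Noncentrality | Power |
|---|---|---|
| 0.36 | 3.11 | 84% |
| 0.5 | 2.24 | 56% |
| 0.8 | 1.40 | 26% |

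So, at SD 0.36, a 0.5-point rise with no crossers is significant more often (84%) than the same rise with two patients over the limit (71%).

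**4. Proportion test.** For k/10 against 0/10, two-sided Fisher p = 2 × C(10,k)/C(20,k). For k = 2 this is 2 × 45/190 = 0.47. For k = 1, 3, 4 and 5 it is 1.00, 0.21, 0.09 and 0.033. Half the arm must cross before Fisher's test is significant. An uncorrected chi-square needs 4/10 (p = 0.025).

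**5. Counts with exact 95% limits.** For 0/n the upper limit is 1 − 0.025^(1/n): 30.8% for 0/10 and 16.8% for 0/20. For 2/10 the interval is 2.5% to 55.6%. If the true crossing rate were 10%, no crossing would be seen among 20 patients with probability 0.9²⁰ = 12%.

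**The case against.** A reader might infer that patients who cross 5% go unnoticed. Section 8.0 does not support that: it has repeated measurement, discontinuation of study drug at the limit, and a DSMB. The gap is in planned analysis and reporting.

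A reader might also infer that the plan forces a comparison of means, or that the harm would be reported wrongly. Neither follows. The section 7.0 sentence allows a chi-square where suitable, and nothing bars a listing of crossings; the documents are silent. The statement about levels under 5% is an expectation, not a claim about every patient, and methemoglobin is named jointly with platelet inhibition.

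On the numbers, it would be wrong to say that crossers hardly move the mean: two of ten at 6% double it, from 1.0% to 2.0%. The t-test fails because the SD grows. The under-1% figure also needs the other patients to show no rise at all, and step 2 shows how quickly that changes. The 84% in step 3 depends on the SD. Finally, a significant small rise is a correct result for a biochemical marker, and the documents do not equate significance with toxicity.

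All of this limits the claim. It does not supply a usable safety analysis: the chi-square option is never tied to the 5% limit, and step 4 shows that it would not help at this size.

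**Conclusion.** The point holds as a gap in the analysis plan that should be closed. Methemoglobin falls by default under a p<0.05 rule, and with 10 per arm neither branch of that rule can support a safety conclusion. The t-test result depends on the unknown SD and on what the non-crossing patients do: for two crossers at SD 0.36, from 0.7% with no rise in the others to about 71% with a 0.5-point rise. Those percentages rest on assumed values and are illustrations. The Fisher p-values and exact limits need only the arm sizes. The practical consequence is that a non-significant result could be read as no harm, when even 0/20 is compatible with a crossing rate of up to 16.8%.

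**What to change.** For the safety conclusion, take methemoglobin out of the general rule in section 7.0 and specify:

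- each patient's peak over the monitored period, listed individually, with median and maximum by arm;
- the number and proportion with a peak of 5% or more, or with study drug stopped for methemoglobin, for each nitrite arm and for both pooled (n = 20), with exact 95% confidence intervals, next to control;
- a safety statement based on those limits, not on p>0.05.

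Mean levels may still be compared as a biochemical marker.

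The monitored period must be settled first. Section 5.0 speaks of intraoperative samples and its table omits methemoglobin, while section 8.0 adds the immediate postoperative period without giving times. These passages must be reconciled.

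The cost is SAP wording, one extra table and an agreed sampling window. No dose or stopping rule changes. The downside is a less favourable safety statement.
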